1.8. SAMPLE SIZE AND POWER

The projected effect size is a 2.0 day difference in the duration of opioid treatment between infants randomized to a rapid-wean intervention and infants randomized to a slow-wean intervention. We derived this sample size by using results from a recently completed trial comparing morphine-treated

infants and methadone-treated infants in which the standard deviation was 6.9 days for the morphine-treated infants and 8.0 days for methadone-treated infants. We used a standard deviation of 6.9 days to derive the sample size, anticipating that more infants will be treated with morphine. However, the primary analysis compares treatment regardless of drug used, and we based our sample size calculation irrespective of the proportion of infants treated with morphine or methadone. **Table 2** is for illustrative purposes only, and shows the number of patients treated with morphine and methadone if 70% of infants receive morphine as the primary opioid treatment.

The study will have two intervention arms (rapid-wean and slow-wean) with 251 morphine/methadone treated infants per intervention arm, for a total of 502 morphine/methadone treated infants. This will achieve 90% power to reject the null hypothesis with a significance level of 0.05 using a two-sided two-sample t-test. The null hypothesis will be morphine or methadone treated infants in both arms will have equal means when the population difference in the duration of opioid treatment is 2.0 days with a standard deviation of 6.9 days. It is difficult to predict the proportion of infants treated with either morphine or methadone in the coming years given potential changes in practice. We will recalculate the sample size by considering the standard deviation from pooled data (without unblinding) after 25% of participant accrual.

Table 2. Sample Size

Intervention Arm	Morphine Treated	Methadone Treated	Total
Rapid-wean	176	75	251
Slow-wean	176	75	251
Total	352	150	502

1.9. PROJECTED RECRUITMENT TIME

We project that enrollment will require 3.3 years based on a targeted enrollment of 502 infants, with 750 infants available each year and a 20% consent rate. This projection assumes that the research team will not change the sample size estimate during the trial.

SECTION 2. CONFLICT OF INTEREST DISCLOSURES

2.1. FINANCIAL CONFLICTS OF INTEREST OF THE INSTITUTIONS AND INVESTIGATORS

The study investigators have no financial conflicts of interest (FCOI) related to the study outlined in this protocol.

2.1.1. Plan for Managing Identified Financial Conflicts of Interests

We will handle any potential or perceived conflicts of interest, including FCOI, per Title 42, Code of Federal Regulations, Part 50, Subpart F (50.604 Responsibilities of Institutions regarding Investigator financial conflicts of interest). This states that institutional officials (and all subrecipients) are required to notify the grants officer of any FCOI prior to expenditure of any funds and within 60 days of any subsequently identified FCOI. The research team will simultaneously notify NICHD, ECHO office, the NRN Steering Committee and the ISPCTN Steering Committee regarding the COI management plan, following institutional guidelines of each participating hospital.

SECTION 3. STATEMENT OF PROBLEM

3.1. PRIMARY HYPOTHESIS OR QUESTION

Among infants receiving an opioid (defined as morphine or methadone) as the primary treatment for NOWS, a rapid-wean intervention will reduce the days of opioid treatment from the first weaning dose to cessation of opioid, compared to a slow-wean intervention.

3.2. SECONDARY OUTCOMES

3.2.1. Secondary Efficacy Outcomes

Secondary Outcome 1_ The numbers of days of opioid treatment from the first weaning dose to cessation of opioid with rapid- and slow-wean interventions among infants treated with morphine.

Secondary Outcome 2_ The numbers of days of opioid treatment from the first weaning dose to cessation of opioid with rapid- and slow-wean interventions among infants treated with methadone.

Secondary Outcome 3_ The proportions of infants in the rapid- and slow-wean intervention arms who have an escalation or resumption of opioid medication during weaning.

Secondary Outcome 4_ The total amounts of opioid from the first weaning dose to cessation of opioid among infants in the rapid- and slow-wean intervention arms.

Secondary Outcome 5_ The initiation and escalation of second- or third-line drugs to treat NOWS signs from the first weaning dose to cessation of opioid in the rapid- and slow-wean intervention arms.

3.2.2. Secondary Safety Outcome

Secondary Outcome 6_ The proportion of infants in each intervention arm with safety outcomes of seizures (clinical or EEG), excessive stool output, respiratory disturbances, and feeding tolerance.

3.2.3. Other Secondary Outcomes

Secondary Outcome 7_ The proportion of infants in each intervention arm with an atypical neurobehavioral profile prior to discharge on the NICU Network Neurobehavioral Scale (NNNS).

Secondary Outcome 8_ The lengths of hospital stay for each intervention arm.

Secondary Outcome 9_ Assessments of maternal well-being and maternal-infant attachment in each intervention arm.

Secondary Outcome 10_ Assessments of growth in each intervention arm.

Secondary Outcome 11_ Assessment of infant wellness after discharge and until 24 months of age in each intervention arm.

Secondary Outcome 12_ Assessment of infant development to 24 months of age in each intervention arm.

3.3. BACKGROUND AND RATIONALE

3.3.1. Public Health Impact

The incidence of maternal opioid use in the United States has increased substantially since 2000 (1). This includes an increase of opioid use during pregnancy including prescription opioids and illicit drugs, as well as a rise in opioid substitution programs for addiction treatment (2). As a consequence of opioid use during pregnancy, the incidence of neonatal opioid withdrawal syndrome (NOWS) has increased five-fold between 2002 and 2012 (1). NOWS is a clinical syndrome that reflects signs of withdrawal from opioids in a newborn following *in-utero* exposure. Signs typically occur in the first 5-7 days following birth and reflect dysfunction of the brain, gastrointestinal tract and autonomic regulation.

Simultaneously during this rise in opioid use, the pattern of use has shifted from an inner city, indigent population to a more socioeconomically diverse population. A systematic literature review indicated rural pregnant women have higher rates of polysubstance abuse, as compared to urban pregnant women (3). The highest incidences of NOWS were reported in the Southeast (i.e., Kentucky, Tennessee, Mississippi, and Alabama) and Northeast (i.e., Maine, New Hampshire, Vermont, Massachusetts and Rhode Island) United States (4). This increase in opioid drugs during pregnancy affects neonatal care across the United States. Multiple cross-sectional analyses show that NICU admission rates for NOWS increased from 7 to 27 cases per 1,000 admissions and that length of stay increased from 13 to 19 days between 2004 through 2013 (5). Mean hospital charges for infants discharged with neonatal abstinence syndrome (NAS) increased from \$39,400 to \$53,400 between 2000 and 2009, and state Medicaid programs bore 78% of these charges (1). The proportion of neonatal hospital costs due to NAS was estimated to rise from 1.6% to 6.7% between 2004 and 2014 among births covered by Medicaid (6). Pregnancy complicated by opioid use disorder is associated with high rates of polydrug use, mental health disorders, infectious diseases, poor nutrition, chronic illnesses, and limited social support (7). Associated risks for newborns beyond NOWS include preterm birth and fetal growth restriction.

Pregnancy represents an opportunity for entry into the healthcare system and initiation of interventions for the mother-infant dyad. However, there are many knowledge gaps in the care of infants with NOWS. The executive summary of a joint workshop by the National Institute of Child Health and Human Development and multiple other partners identified major domains of research priorities on NOWS, including screening and assessment, treatment of NOWS, and transition out of the hospital and follow up (7).

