5.1.3. Other Collected Data

Initial descriptive analyses will include weaning intervention group characteristics. We will collect data to characterize the following.

- Stratification data
- Hospital variables: participation in ESC
- Maternal variables (e.g., socioeconomic status, obstetric complications, opioid medication, medication assisted treatment program, non-opioid drugs, cigarettes, alcohol, selective serotonin reuptake inhibitors, and psychiatric diagnoses)
- Infant demographics at birth (e.g., gestational age, birth weight, sex, multiples, growth parameters, out-born, and location of care)
- Characteristics of NOWS treatment (e.g., stabilization dose, age at stabilization, use of adjunctive drugs to the primary NOWS drug treatment)
- Infant characteristics at the start of the intervention (e.g., weight, postnatal age) and when medically ready for discharge per the hospital standard.

We will include the stratification variable (hospital) in regression modeling as a random effect, and we will include stabilization dose and maternal treatment as covariates. With respect to maternal treatment, it will be a categorical variable with four categories:

- 1) Methadone use
- 2) Buprenorphine \pm naloxone
- 3) Prescribed opioids other than methadone and buprenorphine \pm naloxone
- 4) Non-prescribed opioids

There will be some mixing among these four groups; therefore, we will use the following rules to classify infants:

- If methadone is used with other opioids, classify as methadone.
- If buprenorphine is used with other opioids, classify as buprenorphine \pm naloxone.
- If methadone is used with buprenorphine, classify based on which drug has been in use for a longer time interval.

Depending on the descriptive comparisons across weaning intervention groups, we may add other variables to the regression models such as medication assisted treatment programs. If the difference of a variable across the weaning intervention is statistically significant at a two-sided alpha of 0.05, then we may include the variable as a covariate in the regression models. Beyond the significant difference, we will consider other factors, such as the type of analysis, correlation with other variables in the model, and trial subcommittee discussion about the nature of the potential covariate.

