4.1 Modeling Process

For the primary outcome (H1), linear mixed model with site as random effect and intervention as a fixed effect will be used.

For safety outcomes, binomial proportions and their corresponding 95% CI by intervention arm for seizure (clinical and EEG), excessive stool output, respiratory disturbances, and feeding intolerance will be reported. Chi-square/Fisher exact tests will be used to compare between the intervention arms. If we end up with a very small number of adverse events and severe adverse events, analysis of these measures will be descriptive only.

For the secondary linear outcomes (H2, H3, H5 & H12d), linear mixed model with site as random effect will be used. For secondary binary outcomes (H4, H6), generalized linear mixed model with site as random effect will be used. For count outcomes (H12a-12c), generalized linear mixed models using either Poisson or negative binomial distribution and site as random effect will be used. Intervention will be included in the models as a fixed effect. Secondary outcome models will be adjusted for breastfeeding status, maternal treatment, and stabilization dose.

Hypotheses H9 – H11 will be analyzed in a similar manner to H2. For the PROMIS model (H10), we will adjust for 1-month after discharge and if mother is the primary care giver as fixed effect covariates.

Hypothesis H8 will be analyzed using latent profile analysis as specified in Liu et al. (2). Model fit indices and likelihood ratio tests will inform the determination for the most-appropriate number of classes.

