 μ_i = expected value of outcome y_i

 β_0 = intercept, the expected mean number of treatment days when all covariates = 0

 β_1 = Intervention effect of fast vs slow wean interventions

 $\beta_2, \beta_3, \beta_4$ = effect of maternal treatment, compare to no treatment

 β_5 = effect of stabilization dose

 β_5 = effect of breastfeeding

 β_i = effect of the jth covariate added to the model

For normal outcomes, g(.) is the identity link function.

For binary outcomes, g(.) is the logit link function and we will assume that y_i follows Bernoulli distribution. Alternatively, we can follow Zou et al. (2003) and use the natural log function, and we will assume that y_i follows Poisson or negative binomial distribution. Decision will be based on manuscript writing team, if they prefer to report risks vs odd ratios.

For count outcomes, g(.) is the natural log function, and we will assume that y_i either follows Poisson or negative binomial distribution.

All hypothesis tests will be performed using a two-sided significance level of 0.05. Unless otherwise specified, results for each type regression performed will include the following:

- Normal regression
 - Unadjusted
 - Mean (and 95% confidence intervals (CI)) of the outcome in each treatment group.
 - Mean difference (and 95% CI) of the outcome between treatment groups.
 - Adjusted using pre-specified covariates.
 - Mean (and 95% CI) of the outcome in each treatment group.
 - Mean difference (and 95% CI and p-value) of the outcome between treatment groups.
- Logit Binomial regression
 - Unadjusted
 - Rate (and 95% CI) of the outcome in each treatment group
 - Odds Ratios (and 95% CI) of the outcome between treatment groups
 - Adjusted using pre-specified covariates.
 - Rate (and 95% CI) of the outcome in each treatment group
 - Odds Ratios (and 95% CI and p-value) of the outcome between treatment groups.
- Log-Binomial or Poisson regression
 - Unadjusted
 - Risk (and 95% CI) of the outcome in each treatment group
 - Relative risk (and 95% CI and p-value) of the outcome between treatment groups
 - Adjusted using pre-specified covariates.
 - Risk (and 95% CI) of the outcome in each treatment group
 - Relative risk (and 95% CI and p-value) of the outcome between treatment groups.
- Poisson or negative binomial regression
 - Unadjusted
 - Rate (and 95% CI) of the outcome in each treatment group
 - Relative rate (and 95% CI and p-value) of the outcome between treatment groups

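### The maternal well-being and attachment models (H10) pre-specify no pre-randomisation mental-health covariate, although psychiatric diagnoses and SSRI use are collected; the precision at stake is modest and falls mainly on the 1-month outcomes

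*Protocol*

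**What the plan says.** Protocol 3.3.1 gives the background: pregnancy with opioid use disorder is "associated with high rates of polydrug use, mental health disorders, infectious diseases, poor nutrition, chronic illnesses, and limited social support".

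Protocol 3.2.3 lists as a secondary outcome "Assessments of maternal well-being and maternal-infant attachment in each intervention arm". Table 1 gives PROMIS at 1 month after discharge and at 24 months of age, and MPAQ at 1 month only. Table 3 schedules neither before randomisation. SAP 6.3 repeats these time points, but hypothesis 10A in SAP 2.2.1 tests PROMIS only at 24 months.

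Table 3 places maternal medical history in the baseline collection at randomisation. Protocol 5.1.3 includes among the maternal variables "selective serotonin reuptake inhibitors, and psychiatric diagnoses".

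The pre-specified covariates are:

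- **Protocol 5.1.5:** hospital, maternal opioid treatment and stabilization dose, plus the 1-month score for PROMIS. The models are run in everyone and again where the biologic mother is the main caregiver.
- **SAP 4.1 and 6.4.3:** site as a random effect, breastfeeding, maternal opioid treatment and stabilization dose. SAP 4.1 adds: "For the PROMIS model (H10), we will adjust for 1-month after discharge and if mother is the primary care giver as fixed effect covariates".

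Other variables can enter only through imbalance. Protocol 5.1.3 permits, without requiring, a variable that differs between arms at the 0.05 level. SAP 6.4.3 asks for both clinical and statistical imbalance, and for enough sample.

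**The concern.** PROMIS and MPAQ have no baseline score, so a pre-randomisation predictor has to come from elsewhere. The nearest one, maternal psychiatric history, is already collected but not used. Protocol 3.3.1 says the population has "associated with high rates of polydrug use, mental health disorders, infectious diseases, poor nutrition, chronic illnesses, and limited social support", which makes it a natural candidate.

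The imbalance rule does not fill the gap. It picks covariates by chance difference between arms, not by how well they predict the outcome. A strong predictor that happened to be balanced would stay out, and the choice would be made after seeing data.

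What is at stake is interval width, not validity. It matters most for MPAQ, which has no mental-health covariate of any kind, and for 1-month PROMIS, which cannot be adjusted for itself. At 24 months the PROMIS model already carries the 1-month score.

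**Working it through.** **Step 1. Reproduce the plan's own figures.** Both documents size the trial on the primary outcome only; no power, SD or effect size is stated for H10. Protocol 1.8 assumes that the "population difference in the duration of opioid treatment is 2.0 days with a standard deviation of 6.9 days", with "251 morphine/methadone treated infants per intervention arm, for a total of 502 morphine/methadone treated infants", and states: "This will achieve 90% power to reject the null hypothesis with a significance level of 0.05 using a two-sided two-sample t-test". With n per arm = 2(z₀.₉₇₅ + z_power)²(SD/difference)²:

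- SD 6.9, 90% power: 2 × (1.960 + 1.282)² × (6.9/2)² ≈ 250.1, rounded up to 251 per arm, 502 in total.
- SD 6.2, 90% power (SAP 3.4): 202 per arm, 404 in total.
- SD 6.2, 80% power (SAP 3.4): 2 × (1.960 + 0.842)² × (6.2/2)² ≈ 150.9, rounded up to 151 per arm, 302 in total.

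All three match. For H10 the significance level comes from SAP 6.4.1: "All hypothesis tests will be performed using a two-sided significance level of 0.05".

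**Step 2. MPAQ at 1 month.** Assumed: 302 enrolled (the SAP 3.4 target; final enrolment is not stated), 80% response, 80% power, and R² of 2% to 25% for the indicator.

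- Respondents per arm: 302 × 0.80 / 2 = 120.8.
- Detectable difference without the covariate: 2.802 × √(2/120.8) = 0.360 SD.
- A covariate explaining R² of the variance multiplies the standard error by √(1 − R²).

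| R² | Detectable difference (SD) | Interval narrower by | Power at 0.360 SD |
|---|---|---|---|
| 0 | 0.360 | – | 80% |
| 0.02 | 0.357 | 1% | 81% |
| 0.10 | 0.342 | 5% | 84% |
| 0.25 | 0.312 | 13% | 90% |

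The percentage narrowing depends only on R², so it does not change if fewer mothers respond. The detectable differences do change. An analysis of 1-month PROMIS would be in the same position.

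**Step 3. PROMIS at 24 months.** Assumed: 60% follow-up, borrowed from the Bayley statement in Protocol 5.2.3. That gives 302 × 0.60 / 2 = 90.6 per arm and a detectable difference of 2.802 × √(2/90.6) = 0.416 SD before any score adjustment.

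The 1-month score is already in the model, so what counts is the partial R² of the indicator given that score. Let r be the indicator's correlation with the score (taken as equal at both times) and ρ the correlation between the 1-month and 24-month scores:

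partial R² = (r − rρ)² / [(1 − r²)(1 − ρ²)]

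- r = 0.2, ρ = 0.7: 0.0036 / (0.96 × 0.51) = 0.007; interval 0.4% narrower.
- r = 0.3, ρ = 0.5: 0.0225 / (0.91 × 0.75) = 0.033; interval 1.7% narrower.
- r = 0.5, ρ = 0.4: 0.09 / (0.75 × 0.84) = 0.143; interval 7% narrower.

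Without the 1-month score, r = 0.3 would give R² = 0.09 and a gain of 4.6%. In the middle case, then, the planned adjustment already removes most of what the indicator could add.

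**The case against.** The strongest reply is that this is an optional covariate in an exploratory analysis. SAP 6.4.4 treats everything except the primary analysis as exploratory. Leaving the covariate out biases nothing, and SAP 6.4.2 contemplates dropping covariates if small centres cause convergence trouble. All of that stands and keeps the point minor.

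It is also fair to say that prognostic strength is assumed. Protocol 3.3.1 says mental-health disorders are frequent. It does not say how well a charted diagnosis predicts PROMIS or MPAQ, and a condition that is very common can make a poor any/none indicator. A reader might infer that psychiatric history is a main source of spread in these scores; the documents do not show that.

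A reader might also size the loss from an unadjusted comparison of 24-month PROMIS, where R² of 5%, 10% or 20% is worth 5%, 11% or 25% more respondents (1/(1 − R²) − 1). That is not the planned model. With the 1-month score included and ρ = 0.5, the partial R² values are about 0.018, 0.037 and 0.083, worth about 2%, 4% and 9%. Nor does the 60% follow-up figure document heavy loss for MPAQ: it is a planning condition for the Bayley at 24 months, while MPAQ is a 1-month questionnaire that can be completed electronically or by phone.

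Finally, the diagnoses describe the mother, while the primary caregiver answers PROMIS. The gain is therefore largely confined to biologic mothers. An interaction by respondent type would not be a good way round this, because who responds is known only after randomisation.

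What the reply does not remove is the gap itself. Entry by chance imbalance is not a precision rule, and the data are already in hand.

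**Conclusion.** The point holds as a minor one. H10 has no pre-specified pre-randomisation mental-health covariate, although suitable data are collected at baseline. The likely cost is about 1% to 13% of interval width for MPAQ (and 1-month PROMIS, if analysed), and about 0.4% to 7% for 24-month PROMIS as planned.

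These ranges rest on assumed R² of 2% to 25%, r of 0.2 to 0.5 and ρ of 0.4 to 0.7; none is in the documents. The direction of the effect is clear, but its size is not established.

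Two stronger readings are not supported. The comparison is not biased by the omission. Nor do all secondary models share one generic covariate list, since SAP 4.1 gives PROMIS two terms of its own. Those two terms are measured after randomisation, and conditioning on the 1-month score could absorb part of a treatment effect. That is a separate question, although a psychiatric-history indicator has the merit of not raising it.

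**What to change.** In SAP 6.4.3, before the follow-up analysis that SAP 3.7 expects in July 2026, add one indicator for MPAQ and PROMIS: any recorded maternal psychiatric diagnosis or SSRI use at baseline, against none. Enter it as a fixed covariate whatever the balance between arms, in the biologic-mother analysis set out in Protocol 5.1.5, with no interaction by respondent type. The SAP does not restate that analysis, so the added sentence should name it. It should also say whether 1-month PROMIS is to be analysed as an outcome.

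The cost is one sentence or two of SAP text and one degree of freedom. Under-recorded diagnoses would shrink the gain but would not bias the comparison.

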3.3.2. Background

A recent *Journal of Pediatrics* editorial emphasized the rapid rise of NOWS in the United States and provided a framework to target research initiatives and care delivery innovations for infants with NOWS (8). Specifically, research and quality improvement initiatives should be safe, effective, patient centered, timely, efficient, and equitable. High-quality research is needed to ensure that NOWS care is evidence-based, eliminates non-beneficial practices, and achieves the overarching goals of limiting ongoing opioid exposure for infants, minimizing separation of the mother-infant dyad, and reducing healthcare expenditures. To date, the research community has not rigorously evaluated, through randomized clinical trials, many aspects of NOWS treatment regimens (9).

Signs associated with NOWS reflect dysfunction in several systems: central nervous system (tremors, high-pitched cry, hypertonicity), gastrointestinal (poor feeding, watery, loose stools), and autonomic (hyperthermia). There is widespread acceptance that initial care of infants exposed to opioids *in utero*

should be individualized, supportive, and non-pharmacologic (2). These measures should include minimizing environmental stimuli (e.g., rooming in [10]), encouraging breast-feeding (in the absence of contraindications), and providing sufficient caloric intake. Pharmacological therapy is indicated when signs of NOWS cannot be controlled with non-pharmacological strategies. The objective of pharmacological therapy is to control NOWS signs so that an infant can appropriately bond with her or his mother, tolerate handling and care by healthcare providers, eat effectively with appropriate rest periods to ensure adequate growth, and avoid serious central nervous system dysfunction, such as seizures. Clinical teams traditionally initiate drug treatment when scoring assessments reach a predetermined severity of NOWS signs and include three phases (initiation, stabilization, and weaning). Initiation is the start of drug treatment, and clinical teams progressively increase the dose until the infant achieves stabilization. Stabilization is the interval of time during which the clinical team maintains a drug dose that controls NOWS signs without any indication to further increase the dose. Weaning consists of serial reductions in drug dose and/or lengthening the time interval between doses, and it often begins approximately 48 hours after stabilization. NOWS treatment goals should address four domains: 1) support vital neonatal functions (nutrition, appropriate sleep patterns, etc.), 2) promote family bonding, 3) prevent complications (seizures, excessive weight loss, unmanageable irritability), and 4) provide education for the mother-infant dyad and integration into social services to facilitate a smooth transition out of the hospital (7).

Medical professionals do not universally agree on a standard of care for pharmacologically treated NOWS infants (11). Clinical teams may use different drugs as first-line agents (e.g., morphine, methadone, and buprenorphine) and second-line agents (e.g., phenobarbital, benzodiazepines). At present, morphine is the most commonly used first-line pharmacological treatment for NOWS (12). Cross sectional data from the Pediatrix Clinical Data Warehouse showed that the proportion of infants treated with morphine for NOWS increased from 49% in 2004 to 72% in 2013 (5). Preliminary data from the ACT NOWS Current Experience, a retrospective chart review (Section 3.3.3) conducted among the IDeA States Pediatric Clinical Trials Network (ISPCTN) and Neonatal Research Network (NRN), indicated that morphine was the first-line drug for NOWS treatment in approximately 87% of NOWS infants receiving pharmacological treatment. In contrast, clinical teams used methadone in 13% of pharmacologically treated NOWS infants (**Appendices 1 and 2**).

Quality improvement methods to standardize NOWS treatment have been successful in reducing the length of treatment and hospital stay among NOWS infants (13). In contrast, there are limited randomized clinical trials to guide treatment of NOWS infants who require pharmacological therapy. The trials that do exist compared the duration of treatment with morphine and other pharmacological therapies (14-19); however, these trials were small and collectively included 189 infants treated with morphine and 187 infants treated with phenobarbital, methadone, buprenorphine, or clonidine. There are no clinical trials of different approaches to initiation, stabilization, or the weaning phases of drug therapy. An important rationale for studying weaning of pharmacological treatment for NOWS is that weaning represents the longest time interval of drug treatment. Stopping medications too early may not completely treat NOWS symptoms and may increase the challenges for a family to successfully transition home. Alternatively, excess pharmacological therapy prolongs hospital stay, which increases healthcare utilization and separates the mother-infant dyad.

Kraft et al. summarized the use of morphine and methadone treatment for NOWS (20). Morphine has a relatively short half-life, and medical professionals administer it every three or four hours. Two principal

algorithms for weaning morphine are a percentage reduction (10% of the stabilizing dose every 12-48 hours with cessation at 20% of the stabilizing dose) or a fixed reduction (typically decreases of 0.02 mg morphine/dose each day with cessation at approximately 0.02 mg/dose). Although a standard of care for weaning morphine does not exist, all of the referenced clinical trials weaned morphine by 10% reductions of the stabilizing dose (14-19). However, the research community has not compared weaning by a 10% reduction to a different weaning rate to estimate potential reductions in treatment days without morphine escalation or resumption.

[figure not shown]
Kraft et al. noted that methadone has a longer half-life than morphine and therefore, may be attractive as a therapy due to less frequent administration (20). However, there is inter-subject pharmacokinetic variability in newborns and children receiving methadone (21-22). A pilot study provided important data on the pharmacokinetics of oral methadone for NOWS treatment (22). Medical professionals have used such a pharmacokinetic-based treatment model to initiate treatment (0.1 mg/kg) with 6-hour dosing intervals. If NOWS signs are controlled, they use 12-hour dosing intervals to wean the dose from 0.075 to 0.01 mg/kg in six weaning steps, until a final 24-hour dose interval. If medical professionals do not readily capture NOWS signs at initiation, they use more frequent dosing intervals (4 to 6 to 8 hours) before decreasing doses in 12-hour intervals. The Ohio Perinatal Quality Collaborative regimen has used this dosing schedule in a pre-post intervention study (23).

In contrast to variations for weaning in clinical practice, randomized trials have used 10% reductions of the stabilizing dose. In a single-site trial that compared methadone to morphine, clinical teams weaned both drugs by 10% reductions of the stabilizing dose with four-hour dosing intervals (15). The most recent, and largest (58 infants in each group), randomized clinical trial of NOWS treatment, performed by Davis et al., was a multi-center trial comparing methadone to morphine (18). In this trial, medical professionals weaned NOWS infants treated with methadone or morphine by 10% of the stabilization dose every 12 to 48 hours with cessation of drug therapy at 20% of the stabilization dose. Administration of methadone alternating with placebo every four hours and morphine every four hours facilitated blinding of nursery personnel to the opioid being used. The trial demonstrated that the length of treatment and hospital stay were shorter with methadone, compared to morphine, and these results may prompt a shift from morphine to methadone as the primary opioid to treat NOWS. There are no randomized trials to inform clinicians of potentially better regimens to wean morphine or methadone.

Common outcomes of clinical trials of NOWS treatment are length of treatment, length of hospital stay, and safety outcomes. Although clinically evident brain injury on a neurological exam is not anticipated among infants with NOWS, there is support for abnormalities of neurobehavior (24). Such information may be important to understand maternal well-being after hospital discharge of a NOWS-treated baby. This is an important domain of NOWS research, and there is a growing recognition that outcomes of NOWS investigations need to broaden to include measures beyond length of treatment and length of hospital stay (7).

The NNNS is a comprehensive evaluation of 12 domains of neurologic and behavioral functioning as well as signs of stress, administered by trained, certified examiners (25). The research community has used the NNNS to study multiple groups of high-risk infants, including those exposed to drugs *in utero* (opioids, cocaine) and prematurity (26). Among 1,248 mother-infant dyads enrolled in the Maternal Lifestyle Study, researchers performed NNNS assessments at one month *after* hospital discharge (27). Researchers identified five mutually exclusive neurobehavioral profiles from the 12 neurobehavioral

domains by using latent profile analysis. Profile 5 (black line, **Figure 1**) was the most atypical, and it was characterized by exaggerated scores for arousal, excitability, hypertonicity, quality of movement, and stress abstinence, relative to four other distinct profiles. Researchers have associated Profile 5 with early childhood outcomes, including more externalizing behavior problems, internalizing behavior problems, and total behavior problems at age three, as well as lower IQ scores after adjustment for gestational age and socioeconomic status (27). In this protocol, “atypical neurobehavioral profile” refers to Profile 5 in **Figure 1**.

There is a lack of consensus on the effects of prenatal opioid exposure on neurodevelopmental outcomes in early childhood. A recent comprehensive review indicated that there are discrepant findings with respect to the presence or absence of altered neurodevelopment with in-utero exposure (28). This reflects that many studies are small and cannot adjust for potential confounding variables. Potential confounding variables (e.g., prenatal exposures to other substances, nutrition, socio-economic status, medical complications, poor prenatal care) may all impact early childhood development. Few studies have examined neurodevelopment among infants who develop NOWS, and even less among infants who are pharmacologically treated for NOWS. A retrospective chart review of infants born in 2011-2015 and treated for NOWS with morphine, methadone or buprenorphine had lower Bayley Scales of Infant Development III at 23 months compared with normative data for the Bayley Scales (29). Contemporary data on early childhood neurodevelopment of infants with NOWS in the presence or absence of pharmacologic treatment remains a major research gap.

